We will aim to accrue 20 patients to each cohort, with anticipation of 16 evaluable and operable patients in each. It is estimated that JHH sees between 25-35 patients with stage III resectable NSCLC that would be suitable for enrollment onto this study. We conservatively estimate accrual of 2 patients every month. Accounting for an approximate 10% drop-out rate, we estimate a target accrual of 40 patients in 20-24 months. Additional study sites have been identified that will contribute to accrual, if needed.

List of Tables

Table 1: Selected NSCLC Studies of Adjuvant Chemotherapy Error! Bookmark not defined
Table 2: Trial Treatment Error! Bookmark not defined
Table 3. Highly Effective Methods of Contraception (<1% Failure Rate) Error! Bookmark not defined
Table 4: Supportive Medications Error! Bookmark not defined
Table 5. Prohibited concomitant medications Error! Bookmark not defined
Table 6. Hematology Laboratory Tests Error! Bookmark not defined
Table 7. Clinical chemistry (Serum or Plasma) Laboratory Tests Error! Bookmark not defined
Table 8. Urinalysis Tests ^a Error! Bookmark not defined
Table 9. Volume of blood to be drawn from each subject Error! Bookmark not defined
Table 10.1 Stopping Rule for Safety Error! Bookmark not defined
Table 10.2 Operating characteristics of the stopping rule for safety Error! Bookmark not defined
Table 10.3 Early Stopping Rule for Grade 5 Adverse Event Error! Bookmark not defined
Table 10.4 Operating characteristics of the stopping rule for grade 5 AE Error! Bookmark not defined

List of Figures

Figure 1: Schedule of Assessments	Error! Bookmark not defined.
Figure 2: Study Schema	Error! Bookmark not defined.

List of Appendices

APPENDIX 1. Dosing Modification and Toxicity Management Guidelines for Immune-mediated, Infusion Related, and Non Immune-mediated Reactions (MEDI4736 Monotherapy or Combination therapy with Tremelimumab or Tremelimumab Monotherapy)

Error! Bookmark not defined.

Appendix 3 Schedule of study procedures: follow-up for subjects who have discontinue durvalumab and tremelimumab treatment due to confirmed progression of disease at the investigator discretion...... Error! Bookmark not defined.

Appendix 4: Durvalumab weight-based dose calculation...... Error! Bookmark not defined.

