6.2.2.5. Normal Structures

Normal organs will be contoured as avoidance structures for treatment planning and will include: the spinal canal, the esophagus, the total lung-GTV, and the pericardium

- Spinal Canal: The treatment plan will avoid >50 Gy delivery to the spinal canal
- Esophagus: The treatment plan will keep the mean esophageal dose <34 Gy
- Pericardium: The treatment plan will keep the mean pericardial dose <26 Gy; the point max will be less than 50 Gy.
- Total lung: The total lung-GTV V20 will be <30 Gy. The mean total lung-GTV dose will be <16 Gy. It is strongly encouraged to minimize low dose bath to the total lung, ideally by keeping the V05<55 and the V10<40 to the total lung-GTV. However, these V05 and V10 constraints are not mandatory as situations may arise that required exceeding these constraints to maintain target coverage.

Thoracic radiation will be delivered as per standard of care. If a subject does not complete all planned doses of radiation therapy. The subject will be replaced, but will continue to be followed for safety.

18 Nov 2020 Page **75** of **164**

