6.2.3. Thoracic Surgery

6.2.3.1. Surgical Procedure

- Subjects must be suitable for surgical resection with lobectomy, by an attending thoracic surgeon.
- Subjects only deemed surgically resectable with pneumonectomy by an attending thoracic surgeon, will be excluded from the study.
- If after completion of study therapy a subject is only suitable for surgical resection with a pneumonectomy, the subject will be replaced, but will continue to be followed for safety.

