6.2.3.3. Mediastinal Lymph Node Sampling

• Subjects must have at least 3 mediastinal and hilar lymph node stations sampled during surgery.

If a subject does not receive all planned doses of study therapy and proceeds to surgery, the subject will be replaced, but will continue to be followed for safety.

18 Nov 2020 Page **76** of **164**

J1772, Version 7.0 Date: 20-Jul-2020

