12.1. Study Design

This is an open-label pilot study aimed at establishing the safety and feasibility of neoadjuvant immunoradiation prior to surgical resection of stage III NSCLC, that is deemed surgically resectable by a thoracic surgeon with lobectomy. Thoracic RT will be given at standard doses and fractionation to a total dose of 45Gy in 25 fractions, as per published phase III data⁴⁹, and using standard methods. In cohort 1, the safety and feasibility of durvalumab with concurrent thoracic RT, will be assessed. In this cohort, durvalumab will be administered at the standard dose of 1500mg IV every 4 weeks for 3 doses, as per ongoing phase III studies. If preliminary safety is established in cohort 1, the study will expand to include cohort 2, which will test the safety and feasibility of durvalumab plus tremelimumab with concurrent thoracic RT. In this cohort, durvalumab will be administered at the standard dose of 1500mg IV every 4 weeks for 3 doses, and tremelimumab will be administered at the standard dose of 75mg every 4 weeks for 3 doses. The primary endpoints of this study are safety and feasibility in cohort 1 and cohort 2 (if applicable). Patients will be observed for perioperative grade 3-4 adverse events through day 90 following the last dose of immunotherapy or until 30 days post-surgery, whichever is longer. Safety and feasibility will be monitored continuously throughout the study through weekly meetings with investigators, as well as the planned Bayesian monitoring rules (see below). A set of markers of immune reactivity measured in lung tumor resection specimens, draining lymph nodes, and peripheral blood will be evaluated. Feasibility will be evaluated as the proportion of evaluable patients who successfully complete preoperative treatment and proceed to surgery without any extended treatment related delays. Extended treatment-related delay will be defined as >8 weeks from the day of completion of thoracic RT. For each cohort, we aim to accrue 16 evaluable patients, defined as those who receive at least one dose of durvalumab or durvalumab/tremelimumab administration and have complete toxicity follow-up. We plan to accrue 20 patients to ensure 16 evaluable patients are available for analysis. If less than 16 evaluable patients are available after accruing 20 patients, we will amend the protocol to ensure at least 16 evaluable patients are available for analysis.

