12.2. Study Endpoints Definition

12.2.1. Primary Endpoints

Safety of durvalumab monothererapy (cohort 1) +/- durvalumab+tremelimumab (cohort 2) administered preoperatively together with thoracic radiation in stage III NSCLC.

Safety will be measured by the frequency of any of the following events:

• Drug-related adverse events occurring up to 100 days after the last dose of immunotherapy or 30 days after surgery (whichever is longer).

18-Nov-2020 Page **114** of **164**

- Serious adverse events occurring up to 100 days after the last dose of immunotherapy or 30 days after surgery (whichever is longer).
- Clinical laboratory test by worst toxicity grade (as assessed at the time intervals outlined in the Schedule of Assessments, Figure 1.)

Feasibility of preoperative administration of durvalumab monothererapy (cohort 1) +/- durvalumab+tremelimumab (cohort 2) concurrently with thoracic radiation in stage III NSCLC

Feasibility will be evaluated through the proportion of evaluable patients who successfully complete preoperative treatment and proceed to surgery without any extended treatment-related delays defined as >8 weeks from the last day of thoracic radiation.

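### The co-primary feasibility rate can lose failures from its denominator, because the evaluability and replacement rules are not tied to it

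*Combined protocol and SAP*

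**What the plan says.** Section 12.2.1 defines the co-primary feasibility endpoint as "the proportion of evaluable patients who successfully complete preoperative treatment and proceed to surgery" with no treatment-related delay beyond 8 weeks from the end of thoracic radiation. Completing preoperative treatment is thus part of success. Section 12.1 restricts evaluable patients to "defined as those who receive at least one dose of durvalumab or durvalumab/tremelimumab administration and have complete toxicity follow-up".

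Four replacement rules bear on this:

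- **Leaving early.** Sections 3.1.2 and 6.3 replace patients who do not stay on study through the DLT period. Section 6.3 limits this to reasons other than a DLT. Section 3.1.2 adds that they do not count towards the accrual goal.
- **Radiation.** Section 6.2.2.5: "If a subject does not complete all planned doses of radiation therapy. The subject will be replaced, but will continue to be followed for safety".
- **Pneumonectomy.** Section 6.2.3.1: "If after completion of study therapy a subject is only suitable for surgical resection with a pneumonectomy, the subject will be replaced", again with continued safety follow-up.
- **Missed doses.** Section 6.2.3.3: "If a subject does not receive all planned doses of study therapy and proceeds to surgery, the subject will be replaced", again with continued safety follow-up.

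Section 12.2.3 monitors feasibility from the 6th evaluable patient. The boundary is crossed when the posterior probability of a failure rate above 25% exceeds 70%, under a Beta(0.1, 0.9) prior. The synopsis gives 90% for the same rule. The event counted in Table 10.5 is a delay in planned surgery.

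**The concern.** The patients these rules remove or replace are among those most likely to fail the endpoint. Two mechanisms need to be kept apart.

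The first is written into the plan. A patient who is dosed and then leaves before surgery for a non-DLT reason lacks complete toxicity follow-up, so is not evaluable. Non-completion or absence of surgery may already be on record, yet it never enters the proportion.

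The second is a gap. Section 6.2 replaces three further groups and is silent on whether they stay in the feasibility analysis and in the monitoring count. Sections 3.1.5 and 6.3 lead into one of these groups: patients who cannot receive a dose in the permitted period, and patients with a DLT, stop study therapy and go on to surgery. Section 6.2.3.3 would then replace them, although section 6.3 exempts DLTs from its own replacement rule. Those passages need to be reconciled.

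Feasibility is co-primary, and Figure 2 opens cohort 2 once safety and feasibility are established in cohort 1. The study is open-label, so an unsettled denominator could be settled after outcomes are known.

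**Working it through.** **1. The plan's own figures.** Under Beta(0.1, 0.9), P(risk > 0.25) = 0.142, matching the stated 14% or so. The Table 10.5 boundaries (3 of 6-7, 4 of 8-10, 5 of 11-14, 6 of 15-16) follow from the 70% cut-off except at n = 8, 11 and 15. There, one failure fewer already gives 0.705, 0.735 and 0.706.

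Table 10.6 does not reproduce. An exact sequential binomial calculation on the Table 10.5 boundaries gives these stopping probabilities:

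| True feasibility | 0.65 | 0.70 | 0.75 | 0.80 |
|---|---|---|---|---|
| Table 10.6 | 37.9% | 13.9% | 6.4% | 2.1% |
| Recomputed | 67.7% | 52.8% | 36.8% | 21.8% |

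The same method applied to the safety rule, with boundaries derived from its own prior, gives 16.3 / 29.3 / 44.3 / 59.4 / 72.8% against the stated 15.8 / 29.3 / 43.1 / 60 / 72.8%. The method is therefore sound. The Table 10.6 mismatch is a separate matter and is not evidence for this point; below I use the recomputed values.

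**2. Effect on the estimate.** The posterior after x failures in n patients is Beta(0.1 + x, 0.9 + n - x). Suppose 13 on-time surgeries, 3 delays, and r replaced patients who are all failures. The value of r is my assumption. Accruing 20 to obtain 16 leaves room for up to 4, and the stated 10% drop-out on 20 gives 2.

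| Denominator | Rate | Exact 95% CI | P(failure > 25%) |
|---|---|---|---|
| Replaced patients dropped | 13/16 = 81% | 54-96% | 0.22 |
| All treated, r = 2 | 13/18 = 72% | 47-90% | 0.54 |
| All treated, r = 4 | 13/20 = 65% | 41-85% | 0.80 |

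With r = 4 the posterior passes the 70% cut-off of section 12.2.3 but not the synopsis's 90%. With r = 2 neither is reached. Table 10.5 ends at 16, so for 18 and 20 I apply the posterior criterion itself.

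**3. Effect on the stopping rule.** Let true all-treated feasibility be 0.65 and let a fraction d of failures be dropped. The failure rate among those counted is 0.35(1 - d) / [0.65 + 0.35(1 - d)].

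| d | Failure rate counted | P(stop), Table 10.5 |
|---|---|---|
| 0 | 0.350 | 67.7% |
| 25% | 0.2625/0.9125 = 0.288 | 48.9% |
| 50% | 0.175/0.825 = 0.212 | 25.2% |
| 75% | 0.0875/0.7375 = 0.119 | 5.3% |

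**The case against.** The best defence is section 12.1 itself. Being evaluable needs one dose and complete toxicity follow-up, not full treatment and not surgery. All three section 6.2 rules keep the replaced patient in safety follow-up, and the Figure 1 footnotes and section 8.1.3 provide a safety visit for patients who do not reach surgery or who stop early. On that reading these patients stay in the denominator and count as failures. Nothing in the plan says they leave the feasibility analysis; the remark about not counting in section 3.1.2 concerns early leavers and the accrual goal. This stands as far as it goes: exclusion under section 6.2 is implied, not stated. But if a replaced patient still fills one of the 16 evaluable places, replacement has no function. The defence also does not reach patients who leave the study.

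The direction of bias is also not uniform. Section 6.2.3.3 covers only patients who miss doses and proceed to surgery. Under section 12.2.1 they fail; under the Table 10.5 label, if operated on time, they are not events. If all four replaced patients were of this kind and were scored as successes, the all-treated rate would be 17/20 = 85%, above 81%. Whether a pneumonectomy-only patient is a failure is not defined.

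A reader might infer from the synopsis phrase "with anticipation of 16 evaluable and operable patients in each" that only operable patients are counted. The sentence gives an expected yield from 20 accrued, and the synopsis feasibility table uses evaluable patients. A reader might also divide the true rate by one minus the share of failures dropped. That is wrong: dropping 10% of failures at a true 70% gives 0.70/0.97 = 72%. The quotient 0.70/0.90 = 78% requires 10% of all patients to be dropped, every one a failure.

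Finally, this is a pilot without a hypothesis test, and crossing the boundary pauses the study for review.

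**Conclusion.** The concern holds in limited form: the feasibility rate can lose failures. For treated patients who leave before surgery for a non-DLT reason, the loss follows from the written definition of evaluable. For the section 6.2 replacements, sections 6.2 and 12.1 conflict and the plan does not resolve it. The stronger reading, that the plan already excludes all of these patients, is not supported.

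The size depends on how many patients are affected and how they are scored, which the documents do not give. It ranges from no missed trigger (2 of 18) to a missed 70% trigger (4 of 20). If half the failures were dropped at a true 65%, the chance of stopping would fall from 67.7% to 25.2%. These figures assume that every dropped patient is a failure and that the Table 10.5 boundaries apply as printed. Because this affects a co-primary rate and the rule that guards it, it is more than a missing detail.

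**What to change.** In sections 12.2.1 and 12.2.3:

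- Define the feasibility denominator, for both analysis and monitoring, as every patient who received at least one dose of study drug, whatever the toxicity follow-up or replacement status.
- Score as failures non-completion of preoperative treatment, as section 12.2.1 defines success, and not reaching the planned surgery.
- State how patients who become suitable only for pneumonectomy are scored.
- Align the Table 10.5 event label with that definition.
- State that replacement adds patients and removes none from feasibility.

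The cost is wording only. Replaced patients are already followed for safety, and no extra patients are needed. The reported rate may be less favourable.

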12.2.2. Safety Endpoint

Safety stopping rule:

To minimize the risks of adding durvalumab monotherapy (cohort 1) or durvalumab+tremelimumab (cohort 2) to thoracic radiation prior to surgery, safety will be monitored by a Bayesian stopping rule for the rate of adverse events of interest (Section 9.2). Previous experience with single and multiple dose schedules of durvalumab and durvalumab+tremelimumab demonstrated that the incidence of grade 3-4 toxicities in advanced NSCLC and other solid tumors is low. The primary DLTs of concern for safety monitoring will be grade 3-4 toxicities of the types listed in section 6.3. These include liver, GI, renal, pneumonitis and any other grade 3-4 toxicity that in the opinion of the investigator significantly interfered with the subjects' optimal perioperative management. They will be monitored continuously for sixteen patients through day 90 following the last dose of immunotherapy (or day 30 post-surgery, whichever is longer).

AEs will be monitored continuously for all patients. A Bayesian safety monitoring rule will be used to evaluate the rate of the AE of interest continuously, from the 3rd evaluable patient, and will suspend accrual at any point if there is sufficient evidence of excessive toxicity. Specifically, the Bayesian toxicity monitoring rule will suspend accrual anytime if the posterior probability of AE of interest being larger than 25%, is 70% or higher. We assume a priori that the experimental regimens has an average risk around 5% and there is about 7% chance that the risk will be 25% or higher. This corresponds to a Beta (0.05,0.95) prior distribution. Table 10.1 summarizes the continuous stopping rule for the 16 evaluable patients for each regimen. For example, if 2 patients out of the first 3 or 4 evaluable patients experience adverse events of interest, we will stop accrual. Furthermore, to cautiously assess the toxicity profiles of experimental regimens in the event that accrual is relatively "fast" comparing to the safety assessment duration, the accruals of each cohort will be suspended when 6 eligible patients have been accrued to allow the continuous safety evaluations to be done among the first 6 evaluable patients before further accruals. The accrual would resume only if the following Bayesian stopping rule being used is not met. At any time if the stopping criterion is met, accrual to the trial will be temporarily suspended and the

18-Nov-2020 Page **115** of **164**

principle investigators and study team will review the toxicity data and recommend either modification or termination of the trial.

TABLE 10.1 STOPPING RULE FOR SAFETY

# patients with DLT	2	3	4	6
Out of total # patients treated	3-4	5-7	8-11	16

Table 10.2 summarizes the operating characteristics based on 5,000 simulations with 16 evaluable patients in terms of how frequent the study would stop based on the stopping rule under different hypothetical toxicity rates, as well as the average sample sizes.

TABLE 10.2 OPERATING CHARACTERISTICS OF THE STOPPING RULE FOR SAFETY

Underlying risk	0.15	0.20	0.25	0.30	0.35
% of time study stops	15.8%	29.3%	43.1%	60%	72.8%
Expected sample size	14.3	13	11.7	10	8.6

Early Stopping Plan for Treatment-related Grade 5 AE

We will also evaluate the rate of treatment-related grade 5 AE if it's convincingly greater than 10%. Specifically, the Bayesian toxicity monitoring rule that suspends the accrual anytime if the posterior probability of treatment-related grade 5 AE being larger than 10% is 70% or higher. We assume a priori that the experimental regimens has an average risk 5% and there is about 14% chance that the risk will be 10% or higher. This corresponds to a Beta (0.1,1.9) prior distribution. Table 10.3 summarizes the continuous stopping rule for the 16 evaluable patients for each regimen.

TABLE 10.3 EARLY STOPPING RULE FOR GRADE 5 ADVERSE EVENT

# patients with grade 5 AE	1	2	3
Out of total # evaluable patients	1-3	4-10	11-16

Table 10.4 summarizes the operating characteristics based on 5,000 simulations with 16 evaluable patients in terms of how frequent the study would stop based on the stopping rule under different hypothetical grade 5 AE rates, as well as the average sample sizes.

18-Nov-2020 Page **116** of **164**

TABLE 10.4 OPERATING CHARACTERISTICS OF THE STOPPING RULE FOR GRADE 5 AE

Underlying risk	0.04	0.08	0.10	0.12	0.16	0.20
% of time study stops	6.4%	21.5%	32.2%	38.8%	57.5%	72.4%
Expected sample size	15.5	14.4	13.6	13.1	11.6	10.4

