The co-primary endpoints of this study are safety, tolerability and feasibility in cohort 1, followed by safety and feasibility in cohort 2. Safety will be monitored through the rate of all treated patients that develop adverse events (including serious and non-serious, as well as adverse events of special importance AESIs) and dose-limiting toxicities from commencement of durvalumab/RT or durvalumab/tremelimumab/RT until 30 days postoperatively or 100 days after the last dose of immunotherapy whichever is longer, or any pre-defined pulmonary DLTs that occur from the date of surgery until 30 days postoperatively. The DLT observation window will be defined as the time from the date of commencement of immunotherapy until 30 days post-surgery or 100 days after last immunotherapy dose, whichever is longer. Safety will be monitored continuously for all patients. A Bayesian safety monitoring rule will be used to evaluate the rate of adverse events of interest continuously, from the 3rd evaluable patient, and accrual will be suspended at any time if there is sufficient evidence of excessive toxicity. Specifically, the Bayesian toxicity monitoring rule suspends accrual anytime if the posterior probability of adverse event of interest being larger than 25%, is 70% or higher. The following table gives the corresponding stopping rule for the 16 evaluable patients:

#Patients with DLT	2	3	4	5	6
Out of total #patients treated	3-4	5-7	8-11	12-13	16

Feasibility will be monitored through the proportion of patients who undergo surgery within the planned surgical window: 6-8 weeks after completion of thoracic RT. We will use a probability-based decision rule to decide if the probability of successfully proceeding to surgery as planned is convincingly less than 75%. A Bayesian monitoring rule would apply and suspend the accrual if there is at least 90% probability that less than 75% of patients can continue to surgery without treatment-related delays, as shown in the following table:

#Patients planned for surgical resection	1	2	3	5	6	7	8
resection							
Out of total # evaluable patients	6	7	8-9	10	13	14-15	16

Exploratory analyses as detailed in the biomarker table/summary will be presented descriptively, and are detailed in the researcher comments section.

Sample Size Determination:

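### Table 10.1 gives no safety boundary for 12–15 evaluable patients and the synopsis table gives none for 14–15; the written rule gives 5 of 12–14 and 6 of 15–16

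*Combined protocol and SAP*

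**What the plan says.** Section 12.2.2 defines the rule in words: "the Bayesian toxicity monitoring rule will suspend accrual anytime if the posterior probability of AE of interest being larger than 25%, is 70% or higher". Monitoring is continuous and starts "from the 3rd evaluable patient". The prior has mean 5% with about a 7% chance that the risk is 25% or more: "This corresponds to a Beta (0.05,0.95) prior distribution". The section then says "Table 10.1 summarizes the continuous stopping rule for the 16 evaluable patients for each regimen".

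The table under the title "TABLE 10.1 STOPPING RULE FOR SAFETY" has four columns. Its count row reads "patients with DLT 2 3 4 6", against 3–4, 5–7, 8–11 and 16 patients. There is no column for five DLTs and no entry for 12, 13, 14 or 15 patients.

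The synopsis (Statistical methods) repeats the threshold, "Bayesian toxicity monitoring rule suspends accrual anytime if the posterior probability of adverse event of interest being larger than 25%, is 70% or higher", and introduces its own table: "The following table gives the corresponding stopping rule for the 16 evaluable patients". That table has five columns: 2 of 3–4, 3 of 5–7, 4 of 8–11, 5 of 12–13 and 6 of 16. It has no entry for 14 or 15, and the synopsis does not state the prior.

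**The concern.** A rule that is checked after every patient from the third to the sixteenth needs a boundary at each of those 14 sample sizes. Neither table supplies one, and the two differ at 12 and 13. Two people in the same trial could therefore read different decisions from the same data, depending on which page they opened.

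The gaps do not look deliberate. The companion tables in section 12.2 have no breaks: Table 10.3 runs 1–3, 4–10, 11–16, and Table 10.5 runs 6–7, 8–10, 11–14, 15–16.

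At stake is a suspension and toxicity review that the plan's own criterion calls for. A crossing missed at 13 or 14 may never be recovered. Table 10.1 has no further trigger until patient 16, where it needs six DLTs, so a cohort that stays at five finishes without the review. Safety is a primary endpoint, and the same table governs cohort 2, in which tremelimumab is added.

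**Working it through.** **Inputs.** All come from section 12.2.2: prior Beta(0.05, 0.95), threshold rate 0.25, posterior cut-off 0.70, looks at n = 3 to 16. Tables 10.1 and 10.2 and the synopsis table serve as comparators.

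**Step 1: the prior.** Mean = 0.05/(0.05 + 0.95) = 0.05. P(rate > 0.25) = 0.070. Both match the text.

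**Step 2: the boundary.** With x DLTs in n patients the posterior is Beta(0.05 + x, 0.95 + n − x). The boundary is the smallest x for which P(rate > 0.25) is at least 0.70.

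| n | Boundary | Posterior at the boundary, by n | Table 10.1 | Synopsis |
|---|---|---|---|---|
| 3–4 | 2 | 0.857, 0.755 | 2 | 2 |
| 5–7 | 3 | 0.904, 0.841, 0.769 | 3 | 3 |
| 8–11 | 4 | 0.893, 0.843, 0.786, 0.724 | 4 | 4 |
| 12 | 5 | 0.850 | none | 5 |
| 13 | 5 | 0.802 | none | 5 |
| 14 | 5 | 0.751 | none | none |
| 15 | 6 | 0.858 | none | none |
| 16 | 6 | 0.818 | 6 | 6 |

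Every printed entry is reproduced, so the missing ones can be filled in with confidence. The neighbouring cells confirm the break points: 4 of 12 gives 0.661 and 5 of 15 gives 0.6965, and neither reaches 0.70.

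**Step 3: operating characteristics.** These are exact binomial recursions with outcomes known one patient at a time. Entries are the percentage of trials that stop.

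| True rate | Table 10.2 | Full rule | Table 10.1 as printed | Synopsis as printed |
|---|---|---|---|---|
| 0.15 | 15.8 | 16.3 | 15.8 | 16.0 |
| 0.20 | 29.3 | 29.3 | 28.3 | 28.6 |
| 0.25 | 43.1 | 44.3 | 42.8 | 43.2 |
| 0.30 | 60 | 59.4 | 57.7 | 58.2 |
| 0.35 | 72.8 | 72.8 | 71.1 | 71.6 |

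The full rule comes within 1.2 points of Table 10.2 throughout. Its expected sample sizes are 14.3/13.0/11.5/10.0/8.6, against the stated 14.3/13/11.7/10/8.6. With 5,000 simulations, the standard error at a true rate of 0.30 is √(0.60 × 0.40/5000) = 0.7 points. There the full rule is 0.6 points from the stated 60%, and Table 10.1 as printed is 2.3 points from it.

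**Step 4: which looks are lost.** A trial still open after patient 11 has at most 3 DLTs, so at most 4 at patient 12, where the boundary is 5. A trial still open after patient 14 has at most 4, so at most 5 at patient 15, where the boundary is 6. With sequential outcomes, no first crossing can therefore occur at 12 or 15. First crossings at 13 or 14 occur in 3.0/4.0/4.6% of trials at true rates of 25/30/35%. Table 10.1 misses all of these when they happen. The synopsis table misses only those at 14: 1.9/2.6/2.8%.

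**Step 5: crossings never recovered.** Some missed trials go on to reach 6 of 16. Across true rates from 0.15 to 0.35, the rule is met but the table never triggers in 0.5–1.8% of trials with Table 10.1 and 0.3–1.3% with the synopsis table.

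**The case against.** The strongest reply is that the tables are not the rule. The prose fixes the threshold, and section 12.2.2 gives the prior in full and presents Table 10.1 as a summary. Sections 12.1 and 14.2 place monitoring with the investigators and the study statistician, who can compute a posterior. At 5 of 13 and 5 of 14 the text requires suspension whatever the table omits. This stands. A reader might infer that accrual would continue after five DLTs in 13 or 14 patients. The documents do not support that: the written rule suspends in both cases, and the synopsis table also suspends at 5 of 13. Only 5 of 14 is absent from both tables, and even that is missed only by someone relying on a table alone.

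A reader might also count four unprotected looks in Table 10.1. With outcomes known in sequence, only 13 and 14 can produce a first crossing. Entries at 12 and 15 matter only if several outcomes become known together. That is plausible here, because the DLT window in section 6.3 runs to at least 100 days after the last dose.

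That long window also weakens the practical effect. A last dose near day 60 plus 100 days is about 160 days, or just over five months. At the 1–2 patients per month of section 12.5, roughly 5–10 more patients could enrol before the 13th has complete follow-up. Early DLTs can be counted sooner, but a late boundary has less accrual left to stop. Crossing it brings temporary suspension and review, not automatic termination.

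Finally, a column lost in reading the PDF cannot be wholly excluded for Table 10.1. Its two rows align at four cells, however, and the synopsis table, aligned at five, has its own gap. Extraction loss is therefore an incomplete explanation.

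**Conclusion.** The point holds as an inconsistency between two incomplete summary tables and a fully specified rule. Table 10.1 lacks 12–15, the synopsis table lacks 14–15, and the stated prior and cut-off give 5 of 12–14 and 6 of 15–16.

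The size is modest. Overall stopping probability falls by 0.5–1.8 points with Table 10.1 as printed and by 0.3–1.3 points with the synopsis table. Expected sample size changes by at most 0.11 patients. These figures assume a look after every evaluable patient from the third, outcomes known one at a time, and a team that applies only the printed table.

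It would be wrong to infer that Table 10.2 is invalid. The complete rule reproduces it closely, and better overall than Table 10.1 as printed. This suggests that the simulations used the full boundary and the fault arose in transcription, though the documents do not say so.

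It should still be corrected: as printed, the tables could cost the trial a review that its own criterion requires, and the correction is nearly free.

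**What to change.** Print the same table in section 12.2.2 and in the synopsis, following the rule the plan already states:

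| Patients with DLT (at least) | 2 | 3 | 4 | 5 | 6 |
|---|---|---|---|---|---|
| Out of evaluable patients | 3–4 | 5–7 | 8–11 | 12–14 | 15–16 |

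State beside it that reaching or exceeding the count suspends accrual, and that the posterior criterion governs if table and text ever differ. Add the prior to the synopsis so that its table can be checked there.

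The cost is two replaced tables and a few sentences. The stated rule, sample size, procedures and Table 10.2 need no change.
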